4.1 Objectives

To evaluate the safety and efficacy of lucinactant for inhalation delivered by the next generation ADS device in conjunction with nCPAP, in comparison to nCPAP alone, in preterm neonates with RDS, as assessed by the incidence of and time to respiratory failure due to RDS in the first 72 hours and through 28 days of life, oxygen saturation and use of supplemental oxygen, all-cause mortality through 28 days of life, the incidence of bronchopulmonary dysplasia (BPD) at 36 weeks PMA, and the duration of mechanical ventilation. In addition, this study will evaluate the device performance and the ability to administer up to 3 lucinactant for inhalation repeat treatments.

4.2 Estimand

The primary estimand for this study is the occurrence of intubation for the purpose of mechanical ventilation or surfactant administration in preterm neonates 28 to 32 weeks PMA in the modified intent-to-treat (mITT) population (all randomized subjects that received study medication). Intercurrent events include 1) treatment administration interruptions and 2) intubations for reasons other than MV or surfactant administration. Intercurrent events will be evaluated using the treatment policy, hypothetical, and principal stratum strategies. Details on the implementation of the different strategies are provided in Section 13.

4.3 Efficacy Endpoints

4.3.1 Primary Endpoint

The primary endpoint for this study is the number of subjects with respiratory failure due to RDS or death within the first 28 days of life. Respiratory failure due to RDS is defined as intubation (including intratracheal catheter placement) for MV and/or surfactant administration.

Respiratory failure due to RDS or death will be categorized as follows:

- Early respiratory failure: Respiratory failure or death occurring \leq 72 hours after birth
- Late respiratory failure: Respiratory failure or death occurring $>$ 72 hours and \leq 28 days after birth

Subjects meeting the criteria of respiratory failure due to RDS must continue to be followed for all safety evaluations as outlined in Section 1.2 until the time the subject completes the study or withdraws (Section 10.2).

4.3.2 Key Secondary Endpoints

The key secondary endpoints of this study include the evaluation of the following:

1. Respiratory failure through 72 hours and 28 days of life
2. Time to respiratory failure through 72 hours and 28 days of life
3. BPD and survival without BPD at 36 weeks PMA
4. Severity of BPD at 36 weeks PMA
5. Oxygen saturation and use of supplemental oxygen
6. All-cause mortality through 28 days of life and 36 weeks PMA

4.3.3 Other Secondary Endpoints

Other secondary endpoints of this study include the evaluation of the following:

1. Common complications of prematurity through 36 weeks PMA (IVH, periventricular leukomalacia [PVL], pulmonary hemorrhage, apnea, NEC, patent ductus arteriosus [PDA], acquired sepsis, ROP).
2. Duration of MV and oxygen requirement through 36 weeks PMA
3. Changes in FiO₂, PCO₂, and SpO₂ over the first 72 hours of life, and over the first 7 days of life for FiO₂
4. Number/duration of and reason for re-hospitalization and urgent care visits through 12 months corrected age.
5. Respiratory medications through 12 months corrected age.

4.4 Safety Endpoints

The following safety measures are to be documented in the electronic case report form (eCRF) in accordance with timings outlined in Section 1.2:

1. All-cause mortality through 28 days of life (date and time of death, if applicable)
2. AEs, including adverse device effects (ADEs) and AEs of special interest including AEs during the dosing period, complications related to placement of bi-nasal prongs, and air leak (Section 9). AEs that are ongoing at 36 weeks PMA will be followed for an additional 30 days
3. Concomitant medications (Section 8.6)
4. Use of respiratory support and supplemental O₂ (Section 8.7), including the following:
 - a. Need for endotracheal intubation and MV
 - b. Mode of respiratory support, including oxygen only (without positive pressure)
5. Physical examinations (Section 8.2)
6. Assessments of the following:
 - a) Vital signs (Section 8.1.1)
 - b) O₂ saturation, as determined by pulse oximetry (SpO₂) (Section 8.1.2)
 - c) Chest radiography prior to intubation (Section 8.3)
7. Monitoring of PCO₂ and FiO₂ (Section 8.1.2)

5 STUDY POPULATION SELECTION

5.1 Study Population

This study population will be comprised of preterm neonates $26^{0/7}$ to $32^{6/7}$ completed weeks PMA who are receiving care in a NICU and are receiving nCPAP as the primary support modality for RDS. This study is anticipated to enroll approximately 130 preterm neonates (approximately 50% in each treatment group) who are candidates for SRT and nCPAP. Subjects will be enrolled by strata: subjects $26^{0/7}$ to $28^{6/7}$ completed weeks PMA and subjects $29^{0/7}$ to $32^{6/7}$ completed weeks PMA.

The study population will be randomized in a 1:1 ratio into 1 of 2 treatment groups (see Section 6.4).

5.2 Inclusion Criteria

Each subject must meet all of the following inclusion criteria to be enrolled in this study:

1. Signed ICF from legally authorized representative. Where allowed, it is recommended that consent is obtained antenatally.
2. Gestational age of $26^{0/7}$ to $32^{6/7}$ weeks PMA.
3. Successful implementation of non-invasive support or ventilation within 30 minutes of birth.
4. Spontaneous breathing.
5. Investigator determination of RDS. A chest x-ray should be obtained before treatment to confirm the diagnosis.
6. Within the first 6 hours after birth, requires an nCPAP of 5 to 7 cm H₂O that is clinically indicated for at least 15 minutes with an FiO₂ of ≥ 0.25 to ≤ 0.35 to maintain SpO₂ of 90% to 95%. Transient (< 5 minutes) FiO₂ excursions outside this range do not reset the time requirement.

5.3 Exclusion Criteria

Subjects meeting any of the following exclusion criteria may not be enrolled in this study:

1. A heart rate that cannot be stabilized above 100 bpm within 5 minutes of birth
2. Recurrent episodes of apnea requiring positive pressure ventilation (PPV) administered manually or mechanically through any patient interface
3. A 5-minute Apgar score < 5

4. Major congenital malformation(s) or craniofacial abnormalities that preclude the use of nCPAP, diagnosed antenatally or immediately after birth
5. Clinically significant diseases or conditions other than RDS which could potentially interfere with cardiopulmonary function (eg, congenital heart disease, hydrops fetalis or congenital infection)
6. A known or suspected chromosomal abnormality or syndrome
7. Premature rupture of membranes > 3 weeks
8. Hemodynamic instability requiring vasopressors or steroids for hemodynamic support and/or presumed clinical sepsis
9. A need for intubation and/or invasive MV at any time before enrollment into the study
10. The administration (or plan for administration) of any the following:
 - a) Another investigational agent or investigational medical device
 - b) Any other surfactant agent
 - c) Systemic corticosteroids (other than antenatal steroids)
11. Presence of air leak (pneumothorax, pneumomediastinum, pneumopericardium, subcutaneous emphysema, or definite evidence of PIE) on the baseline chest radiograph, or diagnosed via ultrasound or illumination.

6 STUDY TREATMENT DOSING AND ADMINISTRATION

Preterm neonates who meet all inclusion criteria and no exclusion criteria will be considered to be potential subjects. As soon as study qualification has been confirmed and parental consent obtained, subjects will be randomized to 1 of 2 treatment groups. Time to treatment is potentially an important factor in the success of non-invasive delivery of surfactant. Because of this and other operational factors, antenatal consent should be obtained where permitted. Subjects for which parental consent has been obtained but are not randomized are considered screen failures.

All subjects will receive standard neonatal care in the NICU. Subjects randomized to the active group and the first 2 subjects at each site will receive reconstituted lucinactant delivered via the ADS in conjunction with nCPAP. Subjects randomized to the control group will receive nCPAP only. In order to maintain masking, control subjects will receive “sham” study drug treatment: the ADS will be brought to the bedside but will not be used and no active study drug will be administered. All subjects, including controls, may receive up to 3 repeat treatments if repeat treatment criteria are met. Subjects randomized to the active treatment group may be administered up to an additional 3 treatments of lucinactant for inhalation within 36 hours of randomization. Subjects randomized to control may receive up to an additional 3 sham treatments while receiving nCPAP within 36 hours of randomization.

To maintain masking, study treatment will occur behind a visual barrier. Each site will develop a site-specific blinding plan based upon general procedures provided by Windtree. All staff designated as “blinded” will not be allowed to observe preparation of study materials, setup of the device, or to observe the subject during study treatment through discontinuation and removal of equipment unless an emergent condition develops. The sponsor (as applicable) and the subject’s legally authorized representative will also remain masked. (See also Section 6.6.) For the first 2 open-label active study treatments, blinding procedures should still be followed to ensure the feasibility of the site’s blinding plan.

If at any point during the delivery of lucinactant for inhalation a potential safety risk to the subject is identified, aerosolization must be discontinued and local NICU procedures followed to ensure the safety of the subject. Any significant clinical findings or observations must be documented and communicated to Windtree at the earliest time point possible.

6.1 AEROSURF Delivery System

The ADS creates and delivers aerosolized reconstituted lucinactant via 4 durable modules (Figure 6-1): the touch screen interface (also called the operator interface module), the syringe pump

module, the aerosol delivery module, and the power module; and 3 disposable system elements (Figure 6-2): the cartridge, the aerosol tube set, and the syringe. The ADS is designed for bedside use and is mounted on a wheeled pole for easy transport.

Figure 6-1. The AEROSURF Delivery System – Durable

[figure not shown]
[figure not shown]

Figure 6-2. The AEROSURF Delivery System – Disposables

Details for study drug preparation and ADS operation are provided in the study manual and in the ADS Operator's Manual. Briefly, lyophilized drug is reconstituted immediately before use by adding 10 ml of sterile water for injection to each of 7 vials of lyophilized lucinactant, after which the vials are gently inverted to mix the suspension. The vials are drawn up into the provided syringe, which is then loaded into the syringe pump module. The ADS is brought to the subject's bedside and connected to the subject's nCPAP via the patient interface connector. Carrier gas flow through the ADS is started at 3 L/min while the nCPAP gas flow is reduced by 3 L/min, which allows nCPAP to be maintained during treatment.

The ADS aerosolizes reconstituted lucinactant through heat and pressure created within the cartridge. Together, the 4 modules, along with the disposable system elements, produce, control, and monitor the key elements necessary for the aerosolizing lucinactant.

A complete qualitative risk assessment has been completed to identify and mitigate potential safety risks associated with use of the ADS and is described in the Investigators' Brochure.

6.2 Identity of Investigational Drug Product

The complete list of ingredients for the drug product is shown in [Table 6-1](#).

6.2.1 Formulation of Study Drug

The drug product (lyophilized lucinactant) is supplied as a sterile, white, liposomal powder consisting of a 21-amino acid hydrophobic synthetic peptide, (sinapultide, KL₄ peptide), the phospholipids dipalmitoyl-phosphatidylcholine (DPPC) and palmitoyloleoyl-

phosphatidylglycerol, sodium salt (POPG, Na), and the fatty acid palmitic acid (PA). Immediately before dosing, the lyophilized product is reconstituted with sterile water for injection to a concentration of 30 mg TPL/ml. Reconstituted product should be administered to a study subject (treatment initiated) within 5 hours of reconstitution (33).

Table 6-1. Drug Description

Ingredient	Amount (ml)
Sinapultide	0.862 mg
DPPC	22.50 mg
POPG, Na	7.50 mg
PA	4.05 mg

Note: Amounts reflect reconstituted product at 30 mg TPL/mL

6.2.2 Aerosol characteristics

The emitted dose of the aerosol generated by the ADS is approximately 12.6 mg TPL/min. The mass median aerodynamic diameter (MMAD) of the aerosol is below 5.0 μm , which is considered an appropriate size to be deposited in the alveolus following inhalation. The carrier gas that carries the aerosol to the subject (typically a mixture of air and supplemental oxygen) has a nominal flow rate of 3 L/minute. A disposable fluid trap collects aerosol that condenses within the delivery tubing. Calculations for the theoretical maximum inhaled dose are given in Section 3.2.3.2. The specification for the aerosol temperature at the patient interface is 29 to 41 degrees C.

6.2.3 Packaging and Labeling

Lyophilized lucinactant is supplied in 30-ml glass vials packaged in cartons with foam inserts.

Lyophilized lucinactant and the ADS will be appropriately labeled with the investigational caution statements required by the regional health authority (eg, FDA, EMA) to ensure that users are aware that the product is limited by law to investigational use only.

6.3 Precautions for Aerosol Delivery and Device Usage

The ADS, disposables and study drug are investigational materials which are to be used only for investigational studies with lucinactant for inhalation and not any other purpose. All equipment and supplies are to be returned to Windtree or otherwise destroyed at the end of the study.

Sites must maintain accurate records and proper storage of all delivered and dispensed study drug vials and device components (including the ADS cartridges). Details on study supply accountability and storage are provided in Section 6.9, the study manual, the pharmacy manual, and in the ADS Operator's Manual.

6.3.1 Precautions for Aerosol Delivery

The nCPAP device used during aerosol delivery must be a continuous flow device and have a patient interface, both of which are commercially available for nCPAP delivery to neonates. An unmasked study-trained site designee (eg, respiratory therapist or nurse) must provide close monitoring of the subject and study device during aerosol delivery.

Local NICU policies and procedures for nCPAP delivery are to be used, regardless of treatment group assignment. During study treatment delivery, clinical staff must ensure that the desired level of nCPAP is maintained. Typical maneuvers to improve the delivery of nCPAP (eg, placing an oro- or nasogastric tube, securely but gently immobilizing the subject's head, using pacifiers and/or chin strap), are encouraged during dosing. Subjects must be closely monitored for complications related to placement of the patient interface (see Section 9).

6.3.2 Precautions for Device Usage

Lucinactant for inhalation should be administered only by study staff that are trained on the study protocol, associated procedures on the administration of lucinactant for inhalation, and the subsequent care and monitoring of infants following aerosol exposure. Study personnel must complete all required study training and all local and regional NICU requirements for the operation of an investigational NICU device must be followed. Study infants must be under continuous, close monitoring by trained personnel during and after treatment.

If at any point during set-up, aerosol administration, or at finalization of aerosol delivery, an error screen or audible alarm is generated by the device that may signal a delivery malfunction, the user should follow the on-screen instructions. In most cases, this should resolve the issue and permit users to continue. However, if they are unable to resolve the issue, they must contact previously identified Windtree representative for further instructions (Section 9.3.1). The communication plan included in the study manual will identify users authorized to assist with device problems. In such cases, all local institutional procedures must be followed to ensure continued safety and observation of the subject. The ADS Operator's Manual outlines audible alarms and visual displays that may indicate delivery failure.

If at any time during treatment the safety of the study subject is in question, lucinactant for inhalation must be discontinued, the device must be disconnected and removed from the subject immediately, and local NICU procedures must be followed to ensure the care and safety of the subject. Interventions such as endotracheal intubation, mechanical ventilation, and commercial surfactant administration must be readily available for all study infants being administered lucinactant for inhalation.

6.4 Description of Treatment Groups

The study treatment, 'lucinactant for inhalation,' consists of the investigational drug, reconstituted lucinactant and the ADS. The rationale for the selected device and study treatments, including active and control, is discussed in Section [3.2](#).

6.4.1 Aerosol Delivery in the Active Treatment Groups

Randomization must occur within 6 hours of birth. Study treatment with lucinactant for inhalation must be initiated as soon as possible (within 2 hours of randomization), but no later than 8 hours after birth. For the first 2 subjects at each site and subjects randomized to the active study treatment group, the duration of the initial treatment is 100 minutes (corresponding to 160 mg TPL/kg). The subject will be connected to the study nCPAP and study airway connector (see Section [8.7.3](#)). Following this change in the airway circuit, subjects will need to stabilize for at least 15 minutes before being connected to the ADS.

Subjects are eligible to receive up to 3 repeat treatments (a total of 4 treatments) of the treatment to which they are originally assigned; however, repeat doses for the active treatment will be 80 mg TPL/kg. Repeat treatments will be given as soon as 20 minutes from completion of the previous treatments up to 36 hours after completion of randomization if the subjects meet repeat treatment criteria (Section [6.6](#)). However, all subjects are to receive a repeat treatment, unless the subject is on an FiO₂ of 0.21 (room air) at the end of study treatment dosing (ie, 50 minutes after initiation). Repeat treatments will not be given if it is unsafe to do so in the judgment of the PI.

Preparations for a repeat treatment should begin at the end of the study treatment (eg, reconstituted drug product requested from pharmacy). If a subject is above room air at 100 minutes (or 50 minutes for repeat dosing) after initiation but subsequently is at room air at the time the repeat treatment is ready to be delivered, the dosing team may elect to not deliver the repeat dose. If study drug was reconstituted but not used, it may be used (treatment initiated) up to 5 hours after reconstitution if the subject requalifies within this time. Note that the reconstituted product may only be given to the subject to which it was assigned; it cannot be used for another subject.

The PI will follow routine practice guidelines to determine when a subject in either treatment group requires rescue surfactant therapy or escalation of respiratory support. All study treatments are masked (see Section 6.6).

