6.4.2 Control (“Sham”) Treatment in the Control Group

As described in Section 3.2.2, no inert placebo exists. The optimal control, therefore, is to simulate study drug treatment in a masked fashion by bringing the ADS to the bedside but not administering any study drug, a procedure known as “sham” treatment.

For sham treatment, no active drug will be prepared. Instead, the ADS will be prepared and delivered to the bedside in a masked manner. Masking will occur as with active treatment (eg, behind a curtain). The subject will be connected to the same setup as active subjects (using the study nCPAP and study airway connector; see Section 8.7.3). Following completion of the setup, subjects will need to stabilize for at least 15 minutes. Subjects receiving sham will simulate being connected to nCPAP via the ADS but the ADS itself will not be powered on or connected. The start time for sham treatment (treatment initiation) will be the time at which this simulated connection occurs; the stop time will be 110 minutes later (to account for an approximate 10 minutes to switch the syringe and cartridge in the active treatment group). The subject will remain masked for the same duration as active subjects. As with the active treatment, if the subject’s FiO₂ level is not at room air (0.21) by the end of the “treatment” time, the site should prepare and conduct a repeat “treatment”; each repeat treatment time will be 50 minutes. At the end of the assigned sham treatment time, the subject will be switched to clean nCPAP equipment (if necessary), as occurs at the end of active treatment. Masking equipment may then be removed.

As with active treatment, control/sham treatment is to begin within 2 hours after randomization. Repeat control/sham treatments (up to 3) are to be given if repeat treatment criteria are met, unless it is unsafe to do so in the judgment of the investigator (see Section 6.6). As described in Section 3.2.2, repeat treatment with control/sham in subjects who do not require intubation is ethical.

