6.6 Repeat Treatments

Up to 3 repeat treatments will be administered to each subject, regardless of treatment group assignment, up to 36 hours following randomization. For each subject, repeat treatments will occur if repeat treatment criteria are met, unless it is unsafe to do so in the judgment of the investigator. It is required that all subjects receive a repeat treatment after the previous treatment, unless the subject is on an FiO₂ of 0.21 (room air). Masking procedures used for the initial treatment will be followed for repeat treatments (see Section 6.7).

The repeat treatment criteria are defined as follows:

- Time: \geq 20 minutes from completion of the previous treatment (up to 36 hours following randomization)
- Respiratory support: Subject has a need for $\text{FiO}_2 > 0.21$ to maintain SpO_2 of 90% to 95%.

The repeat treatment should occur as soon as possible after the 20-minute time period has elapsed, but no more than 1 hour after meeting criteria.

As with the initial treatment, the randomization/inventory system will be used to receive the drug kit assignments, and all other procedures that were performed for the initial treatment will be followed for the administration of the repeat treatments.

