6.7 Study Masking

In order to minimize bias in subject assessments, study treatment masking (blinding) will be employed. Details of the masking procedure are provided in the 03-CL-1702 Overall Blinding Plan, Blinding Procedure, Blinding Maintenance and Assurance Plan, and Statistical Analysis Plan documents. The blinding plan is outlined as follows:

- a. In all circumstances, subject safety takes precedence over maintenance of study masking. If at any point masking equipment interferes with emergent patient care or knowledge of study treatment is required for patient management, then the blind should be broken. If this occurs, Windtree must be notified as soon as possible (see Section 9.3.2).
- b. Personnel making or influencing clinical decisions – especially regarding intubation or the level of respiratory support – must be masked from treatment assignment. Every effort should be made to maintain study masking at all times unless the blind needs to be broken for reasons of subject safety. Clinicians may be masked for different subjects at different times, depending on the logistics at each site.
- c. As there are potentially many ways in which treatment assignment might be masked, each site will create a site-specific blinding plan to be followed throughout the study that specifies which staff members (or types of staff members) are masked and which are not, and at what times. This blinding plan must be approved by Windtree prior to subject recruitment.
- d. Operational requirements of blinding are described in the Blinding Procedure document. Generally, active or sham drug syringes and materials will be prepared by an unmasked drug preparer at the time dosing is required and will be obscured from view when

transported to the bedside with the ADS. Once at the bedside, visual barriers will be put in place to block dosing equipment from view outside the immediate bedside area. An unmasked dosing team will then administer active study drug or sham drug treatment. The start time (treatment initiation) for sham will be the time at which the sham setup is complete and the nCPAP circuit is interrupted (to simulate connection to the ADS); the stop time will be 110 minutes later for the initial treatment.

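### The room-air check that triggers a repeat dose is placed at 50 minutes, halfway through the initial treatment, and an unmasked team may decide some repeats under a clause found only in the active-arm section

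*Protocol*

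**What the plan says.** **Length of the initial treatment.** Protocol Section 6.4.1 states that "the duration of the initial treatment is 100 minutes (corresponding to 160 mg TPL/kg"). The synopsis (Section 1.1) describes those 100 minutes as time of aerosol delivery, and Table 6-2 describes two consecutive 50-minute administrations. Repeats last 50 minutes.

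**When room air is checked.**
- Section 6.4.1, second paragraph: all subjects get a repeat unless on room air "at the end of study treatment dosing (ie, 50 minutes after initiation"). The sentence is not restricted to repeat treatments. The synopsis gives the same 50 minutes, as an example, for any active or sham treatment.
- Section 6.4.1, third paragraph: "If a subject is above room air at 100 minutes (or 50 minutes for repeat dosing) after initiation".
- Section 6.4.2 (sham): the check is at the end of the treatment time. For the initial session "the stop time will be 110 minutes later", which allows about 10 minutes for the switch of syringe and cartridge in the active arm.
- Section 6.6: "It is required that all subjects receive a repeat treatment after the previous treatment", unless on room air. The criteria are at least 20 minutes from completion and a need for FiO2 above 0.21. No time from initiation is given.

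**Who may withhold a repeat.** Under Section 6.4.1, if the infant was above room air at the check but is at room air once the repeat is ready, "the dosing team may elect to not deliver the repeat dose". Section 6.7(d) says "An unmasked dosing team will then administer active study drug or sham drug treatment". Section 6.7(b) requires masking of "Personnel making or influencing clinical decisions", above all on intubation and level of respiratory support.

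**SAP.** Section 2.2.2 defines the criterion from completion of the previous dose plus FiO2 above 0.21, and has the reason documented when a qualifying subject is not dosed. Section 3.3.2 summarizes doses received and times qualified by treatment group.

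**The concern.** Two things are at stake.

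The first is whether a repeat is triggered the same way for every infant. Repeat dosing fixes total active exposure, and the ability to give up to three repeats is itself a study objective (Protocol Section 4.1). A site that follows the 50-minute sentence literally makes the decision in the middle of the initial treatment. A site that follows Section 6.6 makes it at least 20 minutes after the end.

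The second is masking. In one situation the choice to dose is left to people who know the assignment, under a clause written into only one arm's section. Under Section 6.6 an infant at room air does not meet the repeat criterion, yet Section 6.4.1 treats dosing that infant as optional rather than excluded. Each treatment also carries at least 6 hours on study nCPAP (Section 8.7.3), so the choice bears on respiratory support as well as dose.

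**Working it through.** **Inputs.** Initial aerosol time 100 min, as 2 × 50 (Section 6.4.1, Table 6-2). Switch about 10 min (Section 6.4.2). Aerosol concentration 4.2 mg TPL/L and minute ventilation 0.4 L/min/kg (Section 3.2.3.2). Initial dose 160 and repeat dose 80 mg TPL/kg, up to three repeats.

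**The plan's own figures.**
- Sham session: 2 × 50 + 10 = 110 min, as stated.
- Theoretical dose: 4.2 × 0.4 × 50 = 84 mg TPL/kg, which the protocol rounds to about 80; 4.2 × 0.4 × 100 = 168, nominally 160.
- Maximum course: 160 + 3 × 80 = 400 mg TPL/kg, matching Section 3.2.3.5.

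**Where each time falls in the initial active treatment.** All times are read as elapsed from initiation, with one 10-minute switch assumed at the midpoint.

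| Elapsed time | Aerosol given | Share of initial dose | Nominal mg TPL/kg | Time to end |
|---|---|---|---|---|
| 50 min | 50 min | 50% | 80 | 60 min |
| 100 min | 50 + (100 − 60) = 90 min | 90% | 144 | about 10 min |
| 110 min | 100 min | 100% | 160 | 0 |

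If 100 minutes means aerosol time, it coincides with 110 elapsed and the arms agree. Section 6.4.1 does not say which is meant: it counts from initiation, which Section 3.1 defines as connection to the ADS. Under either reading, 50 minutes cannot be the end of the initial treatment.

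**What each rule gives for the same infant after the initial treatment.**

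| FiO2 pattern | 6.4.1, 50-minute sentence | 6.4.1, 100-minute sentence | 6.4.2, end of sham session | 6.6, at least 20 min after completion |
|---|---|---|---|---|
| A: above 0.21 at 50 min; room air from 100 min on | Repeat | No repeat | No repeat | No repeat |
| B: room air at 50 min; above 0.21 from 100 min on | Exempt | Repeat | Repeat | Repeat |
| C: above 0.21 through 110 min; room air from 130 min, when the repeat is ready | Repeat | Team may elect | Repeat; no election stated | Criterion not met |

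Patterns A and B show the timing conflict. Pattern C shows the election clause. Section 6.4.2 also refers to the Section 6.6 criteria, so pattern C is unsettled in the sham arm too.

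**Size per decision.** Total active exposure is 160, 240, 320 or 400 mg TPL/kg for 0 to 3 repeats. One decision moves 80 mg TPL/kg, or 80/400 = 20% of the maximum. No document gives how often infants cross room air between these time points, so the number affected cannot be derived.

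**The case against.** Several defences carry weight.

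- **The 110-minute figure is not a rival check time for the active arm.** A reader might infer three competing clocks for one treatment. The documents do not support that: 110 minutes is the sham stop time, built to match 100 aerosol minutes plus the switch. The ADS displays a running count of exposure time (Section 6.10), which makes an aerosol-time reading of 100 natural. What stands is that the text leaves this open and that the 50-minute figure fits neither reading.
- **The election is narrow.** A reader might infer open discretion over dose count. It applies only to infants back at room air. For those still above it, a repeat is required unless judged unsafe by the PI or investigator. What stands is that an unmasked team may also give a dose outside the Section 6.6 criterion. Section 6.7(b) stresses intubation and respiratory support, so the conflict with it is a tension rather than a flat contradiction.
- **The SAP definition is already completion-based.** It carries neither the 50-minute sentence nor the election. FiO2 is recorded every 10 minutes to 150 minutes after the initial start and to 70 minutes for repeats (Section 8.1.2). That covers completion plus 20 minutes in both cases: 110 + 20 = 130 and 50 + 20 = 70. So the count of times qualified cannot be called irreproducible. The SAP still does not name the reading to use, and its documentation rule covers qualified repeats withheld, not repeats given at room air.
- **Bias from drug supply is conjecture.** Unused reconstituted drug may be held for up to 5 hours if the infant requalifies, and the 6-hour nCPAP minimum applies in both arms.

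**Conclusion.** The point holds in two parts. First, the 50-minute wording in Section 6.4.1, echoed in the synopsis, contradicts the 100-minute initial treatment and the 100-minute check in the same section, as well as the completion-based rule in Section 6.6. Followed as written, these give different repeat decisions for the same infant. This rests on the stated durations alone. The further 10-minute difference between arms arises only if 100 minutes means elapsed time. Second, the election clause belongs to an unmasked team, appears only in the active-arm section, and does not fit the FiO2 criterion in Section 6.6 or sit easily with Section 6.7(b).

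The size is 80 mg TPL/kg per decision, in an unknown number of infants. It is tempting to read the 54% to 64% repeat rates in Study 03-CL-1202 as meaning that more than half of infants are affected. Those are infants who received repeats under a different regimen, not infants who returned to room air before a repeat was delivered. A shift of 240 mg TPL/kg through the election would need that narrow circumstance three times in one infant.

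Practical effect is limited: the SAP reports that enrollment stopped at 12 subjects and plans no statistical testing. Dose counts and times qualified are still to be reported by group.

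**What to change.** - **Protocol Sections 1.1, 6.4.1, 6.4.2 and 6.6:** reconcile to one check time, stated relative to completion of the session and applied identically in both arms. Make explicit whether minutes are aerosol or elapsed time.
- **Protocol Sections 6.4.1, 6.6 and 6.7(b):** reconcile the election clause with the FiO2 criterion and the masking requirement, and state whether the clause applies to both arms.
- **SAP Sections 2.2.2 and 3.3.2:** say which recorded FiO2 value defines qualification for a repeat. Beyond the existing record of qualified repeats withheld, record repeats both given and withheld when the infant is at room air.

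Which timing, FiO2 rule or decision-maker is right is for the sponsor to settle. The cost is a short wording change in the protocol and a short addition to the SAP. With enrollment closed, the SAP lines matter for reporting this study, and the protocol wording matters for any later study that reuses the text.
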